4.0 Study-Wide Number of Subjects

4.1 Accrual Goal

Our study-wide accrual goal is 60 evaluable participants. To reach this accrual goal, we will consent and enroll 90 participants as some participants are not able to complete the protocol due to a variety of reasons (e.g., participant does not end up requiring future transfusions). The 60 evaluable participants will be matched 1:1 to historical controls seen between 2015 and 2017, for a total sample size of 120.

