11.0 Data Management and Confidentiality

11.1 Data Analysis Plan

Feasibility

Feasibility will be characterized by calculating (1) the proportion of enrolled patients out of all patients approached, and (2) the proportion of patients who completed both the pre- and post-transfusion QUALMS surveys out of all enrolled patients. A convenience sample of 60 evaluable patients will be enrolled to the study. To reach this goal, we will enroll 90 participants total, with the expectation that some patients will not be able to complete the study protocol, despite being eligible at the time of consent (e.g., do not end up requiring future transfusions). If the observed survey completion rate is 50% (i.e. 30/60), then this observed rate is consistent, with 95% confidence, with the true survey completion rate being as low as 38% or as high as 62%.

Clinical and Utilization Outcomes

To be assessed for clinical and utilization outcomes, participants must have completed a pre-transfusion QUALMS, received an index transfusion, and completed a post-transfusion QUALMS. Each of the 60 enrolled evaluable patients will be matched 1:1 to historical controls seen between 2015 and 2017, for a matched sample size of 120 patients total. Subjects will be matched for transfusion group, IPSS-R, pre-transfusion Hb, and institution). Comparative analyses will be conducted separately by transfusion group. For the transfusion-naive, the primary outcome will be receipt of second transfusion (yes/no) within two months following the first transfusion. For the transfusion-dependent, the primary outcome will be defined as number of units pRBCs received within two months following the next transfusion.

For both groups, we will also compare the number of hospitalizations and clinic visits two months after index transfusion (Table).

PTQA Utilization and Patient-Reported Outcomes

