11.4 Quality Control of Data

We will make every effort to collect all QUALMS data from study participants. RAs will call participants to remind them to complete the questionnaire and to either bring it with them to clinic (pre-transfusion) or mail it back to the site (post-transfusion). We have piloted this technique with 3 patients with MDS at DFCI; all complied. If a QUALMS survey is not complete, the site PI will personally contact each participant. Participants that do not complete the pre-transfusion QUALMS despite personal contact by the PI will be regarded as not having enrolled. We will record all reasons for non-enrollment, and account for all approached participants in the reports.

There may be participants who enroll and complete the pre-transfusion QUALMS, but do not complete the post-transfusion QUALMS. In this case, a PTQA report will not be generated. We will attempt to replace participants who do not complete the post-transfusion questionnaire, although this may prove unfeasible during the two-year timeframe of the study. Whether these participants are replaced or not, we will evaluate the outcomes of these participants, as we may find that there is a change in future transfusion decisions simply from drawing attention to QOL through the pre-transfusion QUALMS. If appropriate, sensitivity analyses will be performed among the subset of patients for whom a PTQA report was generated.

It is possible, although rare, for a patient to die within the two-month follow up period; such patients will be included in analyses based on their clinical and utilization outcomes observed before death.

We will record the number of patients who do not complete the two-month follow up surveys (PTQA utilization, decisional regret, perceptions of care, and perceived stress), and compare patient characteristics between those who do and do not complete the two-month follow up surveys.

**PROTOCOL TITLE: A New Paradigm of Transfusion Decision Support for Patients with MDS:
Using Peri-Transfusion Quality of Life Assessments (PTQAs)**

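### The precision for the survey completion rate is stated on 60 patients, the evaluable target, although the rate is defined over all enrolled patients and 90 are to be enrolled

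*Protocol*

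**What the plan says.** All section numbers refer to the Protocol.

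- **The measure.** Section 11.1 gives the second feasibility result as "the proportion of patients who completed both the pre- and post-transfusion QUALMS surveys out of all enrolled patients". Aim 1 in section 1.1 uses the same base, enrolled participants.
- **The numbers planned.** Section 4.1 says: "To reach this accrual goal, we will consent and enroll 90 participants". Section 11.1 agrees. It states "A convenience sample of 60 evaluable patients will be enrolled to the study" and adds that "we will enroll 90 participants total, with the expectation that some patients will not be able to complete the study protocol".
- **The precision statement.** The next sentence of section 11.1 reads "If the observed survey completion rate is 50% (i.e. 30/60" and gives 95% limits of 38% and 62%.
- **What the 60 are.** For the clinical and utilization outcomes, section 11.1 says "participants must have completed a pre-transfusion QUALMS, received an index transfusion, and completed a post-transfusion QUALMS", and then "Each of the 60 enrolled evaluable patients will be matched 1:1 to historical controls". Section 9.2 defines the index transfusion by completion of both questionnaires. Appendix F describes the goal as 60 completed assessments.
- **What happens to non-completers.** Under section 11.4, a participant who does not return the pre-transfusion survey even after the site investigator has made contact is counted as never enrolled. For those who miss the second survey, it says "We will attempt to replace participants who do not complete the post-transfusion questionnaire", notes that this may not be feasible, and still evaluates their outcomes.

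**The concern.** The definition, the planned enrolment and the worked example stand in one paragraph of section 11.1 and do not agree. The definition and the plan point to a base of 90, and the example uses 60. The 60 is the number meant to remain after losses, and losses are what a completion rate should count.

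The example taken alone would matter little. It matters more beside section 11.4, which drops pre-survey non-completers from the enrolled count. Together the two texts give an analyst written support for a denominator from which some or all failures have been removed. A completion rate on such a base overstates feasibility, and completion is one of only two results that Aim 1 will deliver. The same rule lowers the other result, enrolment yield, because it shrinks the number enrolled out of those approached. One group of patients would thus move both feasibility figures, in opposite directions.

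**Working it through.** **Inputs.** Enrolled: 90 (sections 4.1, 7.1 and 11.1). Evaluable target: 60 (sections 4.1 and 11.1). Illustrated rate: 30/60 = 50%, 95% limits 38% and 62% (section 11.1). The protocol does not name the interval method.

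**Formula.** Wilson interval with z = 1.96:

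centre = (p + z²/2n) / (1 + z²/n)

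half-width = [z / (1 + z²/n)] × √[p(1−p)/n + z²/4n²]

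**Step 1: reproduce the stated figure (30/60).** Here z²/n = 3.8416/60 = 0.0640 and the centre is 0.500. The half-width is (1.96/1.0640) × √(0.25/60 + 3.8416/14,400) = 1.842 × 0.0666 = 0.123. The interval is 37.7% to 62.3%, which rounds to the stated 38% to 62%. The Agresti-Coull and Jeffreys intervals round to the same limits. The Wald (37.3% to 62.7%) and exact (36.8% to 63.2%) intervals round to 37% to 63%. The arithmetic for n=60 is therefore right.

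**Step 2: the same rate on the defined base (45/90).** Here z²/n = 0.0427. The half-width is (1.96/1.0427) × √(0.25/90 + 3.8416/32,400) = 1.880 × 0.0538 = 0.101. The interval is 39.9% to 60.1%. At this rate there are 45 completers, 60 − 45 = 15 short of the evaluable target if evaluable means having completed both surveys.

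**Step 3: the yield the plan implies, if the 60 evaluable are the completers (60/90).** p = 0.667. The centre is (0.6667 + 0.0213)/1.0427 = 0.660. The half-width is 1.880 × √(0.2222/90 + 0.000119) = 1.880 × 0.0509 = 0.096. The interval is 56.4% to 75.6%.

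**Step 4: what the rule in section 11.4 can do to the rate.** Take 90 consented and 60 completing both surveys, and let k of the 30 non-completers be reclassified as never enrolled. The reported rate is 60/(90 − k). The protocol gives no value for k, so the rows below are assumptions that span its range.

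| k (assumed) | Rate | Wilson 95% CI |
|---|---|---|
| 0 | 60/90 = 67% | 56% to 76% |
| 15 | 60/75 = 80% | 70% to 87% |
| 30 | 60/60 = 100% | 94% to 100% |

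Identical conduct of the study could be reported as anything from 67% to 100%, depending on how many losses occur before the first survey is returned.

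**Step 5: the enrolment figures side by side.**

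| Place | Figure |
|---|---|
| 4.1, 7.1, 11.1 | 90 enrolled |
| 23.2 | 90 approached |
| Appendix F | 75 approached (23 + 23 + 29) |
| Appendix H, Accrual Monitoring | 20 per site × 3 sites = 60 accrued |

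Ninety cannot be enrolled if only 75 or 90 are approached, unless in the latter case everyone consents. The base for completion is therefore not fixed even before section 11.4 is applied.

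**The case against.** The strongest reply is that nothing is miscalculated and little turns on the sentence. The interval is right for n=60. A rate of 50% has the largest variance, so it is a usual choice for showing worst-case precision and need not be an accrual forecast. The interval on 60 is slightly wider than on 90, so the protocol does not overclaim. There is no feasibility threshold or go/no-go rule, and the power statements in section 11.2 do not use this sentence. Section 1.1 and section 11.1 both state the denominator correctly, and section 11.4 promises to account for everyone approached, so the counts should be recoverable. All of this stands, and it limits the weight of the point.

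A reader might go further and infer that 30/60 can never be observed, because the 60 are survey completers by definition. The documents do not support that. Evaluable is never defined. The both-surveys condition sits under the clinical outcomes, not under feasibility. The only reason for attrition that the protocol gives as an example is not needing a transfusion. Section 11.4 still evaluates participants without a second survey and treats those with a report as a subset. If evaluable meant only transfused, 30/60 could occur. Section 9.2 and Appendix F favour the completer reading, so the text is in conflict, not settled. On either reading, though, 60 is not the number enrolled.

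The one accrual figure that fits a base of 60 is the 20 per site in Appendix H. It contradicts sections 4.1, 7.1 and 11.1, so it shows that reconciliation is needed and does not rescue the example.

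**Conclusion.** The point holds as a denominator mismatch, not as an arithmetic error. The only precision given for the completion rate is on the evaluable target of 60, while the rate is defined over enrolled patients, planned at 90. On 90, the interval at 50% is 40% to 60% in place of 38% to 62%, a half-width of about 10 points against about 12. At the implied yield of 60/90 it is 56% to 76%. That last figure assumes that the 60 evaluable patients are the completers, which the text suggests but does not state.

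The precision change is minor. The more important part is the rule in section 11.4, which can take pre-survey non-completers out of the base and bias the rate upward. How far depends on the number reclassified, which the protocol does not give. The range from 67% to 100% shown above is the full span, not a forecast. Nor does any section say that the rate will be computed on the 60 evaluable patients, so this is a risk left open by inconsistent text and not a planned error.

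**What to change.** 1. In section 11.1, replace the 30/60 example with figures on 90 enrolled, and name the interval method. With Wilson: 45/90 = 50% (40% to 60%), noting that this leaves only 45 completers; and 60/90 = 67% (56% to 76%), if the 60 evaluable are the completers.
2. State that everyone consented and enrolled stays in the completion denominator, including participants who never return the pre-transfusion survey and those who are replaced.
3. Amend section 11.4 so that its rule on pre-survey non-completers does not apply to this measure.
4. Define evaluable once, and use it consistently in sections 4.1, 9.2, 11.1, 11.4 and Appendix F.
5. Reconcile the numbers approached and enrolled in sections 4.1, 7.1, 11.1 and 23.2, Appendix F and Appendix H.

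The cost is a text amendment. It needs no new patients, data collection or change to the comparative analyses, because consented participants are already recorded.

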9.2 Study Procedures

Please see study schema (Appendix C) for study flow.

Pre-Transfusion

- Once identified by Epic scheduling report, provider suggestion, or study-specific Epic Workbench report, eligible patients will be approached for consent discussion at an appointment with their provider.
 - Patients with Hb approaching 8.5 g/dL will be approached at an appointment prior to an upcoming transfusion.
 - Patients that are transfusion-dependent will be approached at an upcoming appointment with their provider or during a transfusion appointment.
- During this initial encounter, consenting participants will be given a study packet containing a paper copy of the QUALMS. Study participants will be instructed to fill out the survey on the day before their upcoming pRBC transfusion.

**PROTOCOL TITLE: A New Paradigm of Transfusion Decision Support for Patients with MDS:
Using Peri-Transfusion Quality of Life Assessments (PTQAs)**

3. Study participants will indicate whether they would like to receive PTQA reports in person, via mail, or via email.
4. Site RAs will call study participants using script (see Appendix D) on the day prior to an upcoming transfusion to remind them to complete the QUALMS and bring it with them to their transfusion.
5. Note: Index transfusion is defined as any upcoming transfusion appointment for which the participant has completed both the pre- and post-transfusion QUALMS questionnaires.
 - If a participant does not complete the pre-transfusion questionnaire for any reason (i.e., participant forgot to complete at home or forgot to bring in), then the RA may ask the participant to complete the questionnaire at home prior to a subsequent transfusion appointment. This subsequent transfusion will become the index transfusion.
 - If a participant does not complete the pre-transfusion QUALMS at home prior to the appointment and there are extenuating circumstances (i.e., participant does not regularly receive transfusions at the site), then the RA may ask the participant to complete the questionnaire in clinic before his/her planned index transfusion.

Post-Transfusion

6. On the day of transfusion, the site RA will collect the completed pre-transfusion QUALMS survey. Study participants will then receive a second paper copy of the QUALMS, along with a stamped envelope addressed to the appropriate site.

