7. Participants will be instructed to complete this survey exactly one week after transfusion and return it using the pre-addressed, pre-stamped envelope.
8. Site RAs will call participants using script (see Appendix D) to remind them to complete the QUALMS survey exactly one week after transfusion.
 - The window may increase up to one extra week to accommodate for circumstances where the patient is unable to complete the post-transfusion QUALMS (i.e., participant does not feel well or participant forgot).

PTQA Report

9. Once received, the second assessment will be scored and compared with the first, and both the patient and provider will be sent a report with the results. The QUALMS validation study suggested that a clinically meaningful difference on the instrument is between 5 and 10 points;¹² For this study:
 - A post-transfusion score that is within 5 points of the pre-transfusion score will indicate a stable QOL
 - A post-transfusion score that increases by 5 or more points will indicate a clinically significant improvement in QOL
 - A post-transfusion score that decreases by 5 or more points will indicate a clinically significant decline in QOL
10. In our report, we will include language that encourages patient and providers to use these results to inform their next transfusion decision, specifically suggesting that transfusion be halted or decreased in frequency if QOL has worsened.

**PROTOCOL TITLE: A New Paradigm of Transfusion Decision Support for Patients with MDS:
Using Peri-Transfusion Quality of Life Assessments (PTQAs)**

Secondary Outcomes Assessment

11. At 8 weeks post-transfusion, all participants will be sent a survey (Appendix B) to assess the utilization of the PTQA and patients' decisional regret, perceptions of care, and perceived stress.

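### Sections 11.1 and 11.4 fix the main set for the clinical comparisons inconsistently, and requiring the post-transfusion survey selects PTQA participants, but not the described controls, after index.

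*Protocol*

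**What the plan says.** Section 11.1 sets the entry condition for the clinical and utilization comparisons: "participants must have completed a pre-transfusion QUALMS, received an index transfusion, and completed a post-transfusion QUALMS". It then matches the 60 evaluable patients 1:1 to historical controls from 2015 to 2017 on transfusion group, IPSS-R, pre-transfusion Hb and institution. The 30 versus 30 power statements in 11.2 and the goal of 60 completed PTQAs in Appendix F fit this completer set.

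Section 11.4 covers participants who have a pre-transfusion QUALMS but no post-transfusion QUALMS. They get no report, yet "Whether these participants are replaced or not, we will evaluate the outcomes of these participants", on the ground that the first survey alone may change transfusion decisions. It adds that, if appropriate, "sensitivity analyses will be performed among the subset of patients for whom a PTQA report was generated". Those without the first survey drop out altogether: "Participants that do not complete the pre-transfusion QUALMS despite personal contact by the PI will be regarded as not having enrolled". Section 13.3 provides for continued outcome collection, with permission, from participants who forgo the second survey.

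The note in section 9.2 reads "Index transfusion is defined as any upcoming transfusion appointment for which the participant has completed both the pre- and post-transfusion QUALMS questionnaires". On timing, "Participants will be instructed to complete this survey exactly one week after transfusion", and "The window may increase up to one extra week"; feeling unwell and forgetting are the examples given for the extension. Section 8.1 counts the primary outcomes over 8 weeks from the index transfusion.

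**The concern.** Two sections give different answers to whether a participant without the second survey belongs in the clinical comparison. Every primary comparison could then be run on either set, and the choice could be made after the results are known.

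The 11.1 condition is also met only after follow-up has begun. A PTQA participant enters the comparison only by returning a survey one to two weeks after index, while no matching condition is described for controls. If people who are unwell return the survey less often, part of any difference from controls, for example in hospitalizations, may reflect who responded and not the effect of PTQA. The 9.2 note builds the same condition into the definition of index.

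**Working it through.** **1. Which participants each section admits**

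| Participant | 11.1 | 11.4 |
|---|---|---|
| No pre-QUALMS | Out | Regarded as not enrolled |
| Pre-QUALMS, transfused, no post-QUALMS | Out | Outcomes evaluated |
| Pre-QUALMS, transfused, post-QUALMS (report generated) | In | In; also the sensitivity subset |

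A report requires the second survey, so the 11.4 sensitivity subset is the 11.1 set. A sensitivity analysis on that subset makes sense only if the main set is wider. 11.4 does not say that its non-completers were transfused; the second row assumes it, since outcomes run from a transfusion. If nobody misses the second survey, the two sets are identical.

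**2. When the condition applies**

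The outcome window is 8 × 7 = 56 days. The survey falls at 7/56 = 12.5% to 14/56 = 25% of it.

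**3. Size of the selection**

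This would need the rate of second-survey non-completion among transfused participants, and their outcomes. The protocol gives neither. The step from 90 enrolled to 60 evaluable cannot stand in for it, because it also covers patients who were never transfused.

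**4. The stated power, reproduced at 30 per group (two-sided 5% assumed)**

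- Units: z = d/(SD·√(2/n)) = 1.5/(2.0 × √(2/30)) = 2.905; power = Φ(2.905 − 1.96) = 82.8%, against 83% stated.
- Second transfusion, continuity-corrected z: power = Φ{[(d − 1/n)√n − 1.96√(2p̄(1 − p̄))] / √(p₁q₁ + p₂q₂)}. With p₁ = 1.00, p₂ = 0.70, d = 0.30 and p̄ = 0.85 this gives 84.8%, against 85% stated. Fisher's exact test gives 92.3%.

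**5. Cost of the wider set**

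Assume that a share f of analysed participants has no report and no effect. The unit difference becomes 1.5(1 − f), and the PTQA second-transfusion rate becomes 0.70(1 − f) + 1.00f. SD is held at 2.0.

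| f | n per group | Unit difference | Power, units | PTQA rate | Power, corrected z | Power, Fisher |
|---|---|---|---|---|---|---|
| 0 | 30 | 1.50 | 83% | 0.70 | 85% | 92% |
| 10% | 30 | 1.35 | 74% | 0.73 | 78% | 86% |
| 20% | 30 | 1.20 | 64% | 0.76 | 71% | 76% |
| 10% | 33 | 1.35 | 78% | 0.73 | 83% | 91% |
| 20% | 38 | 1.20 | 74% | 0.76 | 84% | 92% |

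The last two rows keep 30 completers per group: 30/0.9 = 33.3 and 30/0.8 = 37.5, taken as 33 and 38.

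**6. Cost of a landmark**

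Counting outcomes only from day 7 or day 14 leaves 49 or 42 days. If the effect on units scales with time and SD stays 2.0 (both assumed), the difference is 1.5 × 49/56 = 1.31 or 1.5 × 42/56 = 1.125, and power is about 72% or 59%. If the effect arises only after the report, the loss is smaller.

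**The case against.** The strongest defence is that 11.4 describes a supplementary look. It names no main set, its sensitivity analysis is conditional, and its stated interest is whether the first survey alone changes decisions. The evaluable target and the power statement both point to completers. So a reader who infers that the two sections explicitly swap main and sensitivity roles goes beyond the text. What stands is that 11.1 excludes these participants, 11.4 evaluates them without calling this supplementary, and the only set that 11.4 labels as sensitivity is the 11.1 set.

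A reader might also infer from the 9.2 note that the 11.4 analysis cannot be run. That is too strong. The transfusion date is known, the same note speaks of a planned index transfusion before any second survey exists, and 11.1 lists index transfusion and second survey as separate conditions. The definition is a drafting flaw with an obvious repair.

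A third tempting reading is that survival to the survey biases the result substantially or in a known direction. The protocol does not support this. Section 11.4 calls death within two months rare and includes such patients on outcomes before death. The direction is open: early deaths among controls would lower their unit counts and work against PTQA, while losing participants too ill to respond could lower PTQA hospitalizations and work in its favour. Reminder calls, the extra week and the rule "If a QUALMS survey is not complete, the site PI will personally contact each participant" reduce non-response but do not exclude it.

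Finally, detailed eligibility rules for controls may sit in a statistical analysis plan that is not shown. The one-sidedness therefore holds for the controls as the protocol describes them.

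**Conclusion.** The point holds as an inconsistency that should be fixed. The protocol sets the population for its clinical comparisons in two ways that disagree on participants without a second survey, and it defines index by an event 7 to 14 days later. The resulting selection applies to the PTQA group and not to the controls as described. Illness-related non-response is the main concern; early death is a minor one by the protocol's own account. Neither the size nor the direction of the selection can be derived. The power figures in 11.2 are not in error: both reproduce at 30 completers per group. The dilution figures rest on assumed shares of 10% and 20% without a report, and on no effect at all in those participants.

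**What to change.** 1. In 9.2, define the index transfusion when it occurs, as a transfusion preceded by a completed pre-transfusion QUALMS, and delete the post-transfusion condition from the note.

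2. Make 11.1 and 11.4 agree by naming one main set, and the other as the sensitivity set, before outcomes are seen.
   - Participants with a first survey and an index transfusion, whether or not they returned the second, form the set that avoids the one-sided selection after index. Its cost is the dilution shown above, to be stated beside the 11.2 figures. The concern is smaller for second transfusion if Fisher's exact test is used, since power there starts near 92%. Keeping 30 completers per group recovers part of the loss for units, and control reviews rise from 60 to 66 or 76 under the assumed shares.
   - If the sponsor keeps completers, in line with the 60 evaluable and the 30 versus 30 power, report the wider set as the sensitivity analysis and state the selection as a limitation. This costs wording only.

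3. A landmark applied to both groups may be added as a sensitivity analysis only. It equalises survival but not response, since controls return no survey, and it shortens the 8-week window of 8.1.

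4. As wording, refer to the index transfusion in 11.1 where it now speaks of the first or next one, to agree with 8.1.
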